# **5.7.3 Dose-limiting Toxicity**

A DLT is defined as:

- Any life-threatening toxicity;
- ALT and AST levels  $\geq 5 \times ULN$  or total bilirubin  $\geq 2.0 \text{ mg/dL}$ ;
- An infusion reaction that requires hospitalization, despite premedication;
- Any other toxicity which in the opinion of the SRC would have precluded further dosing.

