#### 7.2.7.2 Liver Function Tests

Blood for LFTs is to be collected at Screening, pre-dose on Day 0 (unless the screening evaluations were performed within the previous 72 hours) and Day 28, and at the Day 1, 2, 7, 14, 29, 30, 35, 42, and 56 study visits (or Days 1, 2, 7, 14, 22, 23, 28, 35, and 56 for optional cohorts dosed once every 3 weeks), or at the time of early termination, if applicable. These samples are to be processed at the site's local laboratory.

Prior to discharge from the hospital on Days 1 and 29 (or Days 1 and 22 for optional cohorts dosed once every 3 weeks), local LFTs must be reviewed by the Investigator and the results deemed not clinically significant. Any clinically significant findings must be discussed with the medical monitor to determine whether patient can be discharged and to formulate plans for patient follow-up.

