1.2.5.2. Safety Parameters

Safety monitoring will include assessment of adverse events (AEs), 12-lead ECGs, cardiac monitoring (telemetry), arterial oxygen saturation (SaO₂) using pulse oximetry, vital signs (blood pressure, pulse rate, oral body temperature, and respiratory rate), clinical laboratory safety tests (hematology, serum chemistry, LFTs, thyroid function parameters, serology, coagulation parameters, urinalysis, cytokines, c-reactive protein [CRP], and complement factors), and physical examinations. Patients will be closely monitored for both acute and delayed IRRs. All IRRs will be recorded as AEs.

The safety of ALN-TTR02 will be evaluated by:

- The proportion of subjects experiencing AEs, serious adverse events (SAEs), DLTs, infusion-related AEs, and AEs leading to study drug discontinuation.
- Infusion tolerability, as assessed by serial ECGs, measurement of SaO₂ by pulse oximetry, and blood pressure.
- Change from baseline in clinical laboratory test results, including hematology, serum chemistries, LFTs, and coagulation parameters.
- Change from baseline in measures of thyroid function (thyroid stimulating hormone [TSH], T4, and triiodothyronine [T3]).
- Change from baseline in CRP, cytokines, and complement.
- Vital sign measurements.
- Physical examination findings.

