4.5.2. Adverse Events

Adverse events will be displayed in tables and data listings using MedDRA system organ class (SOC) and preferred term.

Analyses of AEs will be performed for those events that are considered treatment-emergent, where treatment-emergent is defined per protocol as any AE with onset during or after the administration of study medication through 28 days after dosing, or any event that was present pre-infusion but worsened in intensity or was subsequently considered drug-related by the Investigator.

When determining whether an AE is treatment-emergent, partial dates will be handled as follows. If the day of the month is missing, the onset day will be set to the first day of the month unless it is the same month and year as study treatment. In this case, in order to conservatively report the event as treatment-emergent, the onset date will be assumed to be the date of treatment. If the onset day and month are both missing, the day and month will be assumed to be January 1, unless the event occurred in the same year as the study treatment. In this case, the event onset will be imputed as the day of treatment, in order to report the event conservatively as treatment-emergent. A missing onset date will be imputed as the day of treatment. If the resulting imputed onset date is later than a non-missing date of resolution, then the imputed onset date will be set to the resolution date. The imputed data is used solely for the purpose of determining whether an AE is treatment-emergent; actual dates as recorded on the eCRF will be presented in subject listings.

Adverse events are summarized by subject incidence rates; therefore, in any tabulation, a subject contributes only once to the count for a given SOC or preferred term.

The numbers and percentages of subjects with any treatment-emergent adverse event (TEAE), with any TEAE assessed by the Investigator as related to treatment (definitely or possibly related), with any TEAE that is severe in intensity, with any serious TEAE, with any TEAE leading to discontinuation of study medication, or with any TEAE considered a DLT will be summarized by dose group and overall.

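### The DLT count is limited to treatment-emergent events, so in the 3-week cohorts a new-onset DLT dated to the Day 56 liver test would be listed but not counted

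*SAP*

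**What the plan says.** Protocol 5.7.3 opens with "A DLT is defined as" and gives four criteria: life-threatening toxicity, liver enzyme or bilirubin thresholds, an infusion reaction needing hospitalization, and "Any other toxicity which in the opinion of the SRC would have precluded further dosing". None has a time window or requires the event to be treatment-emergent.

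SAP 1.2.5.2 says safety will be evaluated by, among other items, "The proportion of subjects experiencing AEs, serious adverse events (SAEs), DLTs, infusion-related AEs, and AEs leading to study drug discontinuation". No limit is placed on DLTs there either.

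SAP 4.5.2 narrows this. The summary gives the number and percentage of patients "with any TEAE considered a DLT will be summarized by dose group and overall". Treatment-emergent has two arms. The first is "any AE with onset during or after the administration of study medication through 28 days after dosing". The second is "or any event that was present pre-infusion but worsened in intensity or was subsequently considered drug-related by the Investigator", which has no day limit. SAP 4.5.2 also plans a by-subject DLT listing (Table 14.3.2.4), for which no treatment-emergent restriction is stated.

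For the 3-week cohorts, Protocol 7.2.7.2 schedules liver tests on "or Days 1, 2, 7, 14, 22, 23, 28, 35, and 56 for optional cohorts dosed once every 3 weeks". Protocol 8.5 states the adverse event period as 28 days after the last dose and equates that with Day 56 for patients who receive both doses. Protocol 8.4 has adverse events reported through Day 56.

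**The concern.** The count and the definition it is meant to summarize do not cover the same events. The 28-day limit fits the 4-week schedule, where dose 2 plus 28 days is Day 56. It was not adapted when 3-week cohorts were added, although their final visit stayed at Day 56. Data from that visit are collected, but a new event dated there falls outside the period used for counting.

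This affects a result tied to the primary objective of safety and tolerability. The DLT listing and the DLT row of the summary table could disagree within the same report. The two regimens would also be counted over different parts of their follow-up, although the study is meant to supply the recommended Phase 3 dose and regimen.

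**Working it through.** **Inputs**
- Dose 2: Day 28 (+2 days) in 4-week cohorts; Day 21 (+2 days) in 3-week cohorts (Protocol Tables 1-1 and 12-1).
- Last scheduled liver test: Day 56 ±3, so Day 53 to 59, in both regimens (Protocol 6.3.8 and 7.2.7.2).
- Liver test before it: Day 42 ±3 (4-week) or Day 35 ±3 (3-week).
- First arm of treatment-emergent: onset within 28 days after dosing (SAP 4.5.2).
- Up to four optional cohorts of 3 patients may use 3-week dosing (Protocol Appendix 4): 4 × 3 = 12 patients at most.

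**Step 1: the protocol's own figure.** Protocol 8.5 equates 28 days after the last dose with Day 56. For 4-week dosing, 28 + 28 = 56, which reproduces. For 3-week dosing, 21 + 28 = 49, or 23 + 28 = 51 with the +2-day allowance. It does not reproduce.

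**Step 2: days from dose 2 to each test (test day minus dose-2 day).**

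| | 4-week | 3-week |
|---|---|---|
| 28 days end on | Day 56 to 58 | Day 49 to 51 |
| Day 56 test, nominal | 56 − 28 = 28 | 56 − 21 = 35 |
| Day 56 test, shortest | 53 − 30 = 23 | 53 − 23 = 30 |
| Day 56 test, longest | 59 − 28 = 31 | 59 − 21 = 38 |
| Previous test, shortest | 39 − 30 = 9 | 32 − 23 = 9 |
| Previous test, longest | 45 − 28 = 17 | 38 − 21 = 17 |

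**Step 3: how often the Day 56 test lies within 28 days.** Three dose-2 days and seven visit days give 3 × 7 = 21 combinations.
- 4-week: dose 2 on Day 28, 29 or 30 leaves 3, 2 or 1 visit days beyond 28 days. That is 6 outside and 15 inside.
- 3-week: even the shortest interval is 30 days, so all 21 are outside.

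**Step 4: what lies between the tests.** In the 3-week cohorts no liver test is scheduled between Day 35 ±3 and Day 56 ±3. From day 18 after dose 2 to the end of the 28 days there is none. On scheduled tests alone, a rise in that interval would first be seen at the visit that falls outside.

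**Step 5: size of one omitted event.** SAP 3.5 pools cohorts with the same dose level and regimen; SAP 3.2 also separates dose groups by premedication. The denominator can therefore run from 3 to 12: 1/3 = 33%, 1/6 = 17%, 1/9 = 11%, 1/12 = 8%. In the overall column with full enrollment it is 1/27 = 4%.

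**The case against.** A reader might infer that a DLT counts only if it begins within 28 days, so that every Day 56 liver DLT in these cohorts is always excluded. The documents do not support that.

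- The second arm of the definition has no day limit. Patients may enter with AST and ALT up to 2.5 × ULN, so an elevation present before infusion that worsens to DLT level at Day 56 is treatment-emergent and is counted. This route is unlikely for bilirubin, which must be normal at entry.
- Exclusion requires onset to be dated to the test. The documents give no onset rule for laboratory events, and an earlier recorded onset would bring the event in. So would a blank one: "A missing onset date will be imputed as the day of treatment". That rule does not help an event carrying its known test date, and Protocol 8.7, which asks for distinct onset dates when severity changes over days, makes Day 56 dating plausible.
- SAP 4.5.2 says its definition follows the protocol, and Protocol 8.5 reads 28 days as Day 56. On that reading the visit is inside the period. For 3-week dosing, however, the two statements cannot both be true, and the SAP's wording is 28 days. The ambiguity affects every treatment-emergent row, not DLTs alone.

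It might also be inferred that safety decisions would change or that the event would be lost. Neither follows. The stopping rule acts on any DLT through Safety Review Committee review, not on this table. The event would remain in the DLT listing, the full adverse event listing, the abnormal laboratory listing, the dose-2 shift table and the individual liver plots. Nor is there a practical gap from requiring an adverse event: Protocol 8.1 and 8.3 make laboratory findings recordable as such.

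These objections limit how often the omission would occur and what it would affect. They do not remove the mismatch between definition and count.

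**Conclusion.** The point holds in a limited form. Read literally, SAP 4.5.2 leaves out of the only tabulated DLT count a new-onset DLT that is first seen at, and dated to, the Day 56 liver test in a 3-week cohort. The same visit usually counts in a 4-week cohort.

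This rests on four conditions: a 3-week cohort is enrolled; visits stay within their windows; the event was not present before infusion; and its onset is recorded as the test date. Twelve patients is the maximum, reached only if all four eligible optional cohorts use 3-week dosing. A fall from 33% to 0% is the single-cohort extreme; with pooling the change can be as small as 8 percentage points.

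The consequence is a possible disagreement between count and listing and an uneven comparison of regimens in the report. Conduct of the trial is not affected. The correction is worth making because the DLT proportion is a named safety measure and the data are already collected.

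**What to change.** In SAP 4.5.2 and Table 14.3.1.1, count every patient with an event meeting Protocol 5.7.3, whatever its treatment-emergent status. Do not add committee confirmation as a general condition, since only the fourth criterion depends on the committee's opinion. State that the count must agree with Table 14.3.2.4.

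Show days since the most recent dose for each DLT. Removing the limit leaves unequal nominal follow-up from dose 2 to Day 56 (35 days in 3-week cohorts, 28 in 4-week cohorts), and this lets the reader see it.

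Reconcile the 28-day and Day 56 statements in Protocol 8.5 and SAP 4.5.2 for the 3-week regimen, since the same ambiguity reaches the other treatment-emergent rows.

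The cost is wording in the SAP, a clarification in the protocol and a small change to table programming. No new data are needed.

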4.5.3. Laboratory Data

Clinical laboratory values will be expressed in SI units.

Descriptive statistics will be provided for the actual values and changes from baseline to each on-study evaluation for each clinical laboratory parameter, including hematology, clinical chemistry, LFTs, thyroid function tests, and coagulation studies. Percent change from baseline will also be summarized.

Descriptive statistics will be provided for CRP and cytokines at pre-dose and 2, 6, and 24 hours post-dose. Change from pre-dose will also be summarized. Fold change, as defined below, will be summarized for CRP. Complement factor (Bb) will be summarized at pre-dose, and 30 minutes, 2 hours and 24 hours post-dose. Change and fold change from pre-dose will also be summarized. Separate summaries will be presented for Dose 1 and Dose 2.

Fold change from pre-dose is defined as the ratio of the post-dose value to the pre-dose value. Maximum fold change is defined as the ratio of the maximum post-dose value to the pre-dose value. Maximum fold change from pre-dose for cytokines, complement factor (Bb), and CRP will be represented graphically in the form of a semi- \log_{10} plot. Maximum fold change will be plotted for each subject, grouped by dose level. Data recorded as below the limit of detection will be set equal the lower limit of detection for the calculation of fold change. Separate plots will be presented for Dose 1 and Dose 2.

For each continuous laboratory parameter, results will be categorized as low, normal, or high based on the laboratory normal ranges. Shift tables will be employed to summarize the pre-dose category versus the post-dose category, where the post-dose category will be based on the maximum observed value (in absolute value) subsequent to each dose. For dose 1, the maximum value shall be selected from assessments performed through the Day 28 pre-dose

value (Day 21 for the 3-week regimen). All out-of-range and clinically significant laboratory results will be identified in subject data listings.

Figures will be produced for each dose group that display each subject's AST, ALT, alkaline phosphatase, and bilirubin (total and direct) results over time; 1 figure will be produced for each dose group and liver function test parameter, with lines presenting subject results over time. In addition, treatment group means, with standard error bars, will be plotted over time. Similar plots will be produced for complement factor (Bb) and cytokines. A vertical reference line will identify the nominal Dose 2 dosing day (i.e., Day 28 for the 4-week regimen or Day 21 for the 3-week regimen).

Urinalysis results will be included in subject listings but will not be included in summary tables.

Tryptase and C3a will be included in subject listings for any subjects experiencing an IRR.

Results of anti-PEG antibody testing will be listed if any positive results are reported.

All laboratory data, including the Day 0 fasting lipid panel, will be provided in data listings.

Laboratory values outside of the normal ranges will be listed separately, together with comments as to their clinical significance.

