# 7.2.7 Clinical Laboratory Tests

Laboratory tests of hematology, serum chemistries, liver function, coagulation studies, CRP, urinalysis, pregnancy (serum and urine), hepatitis B and C serologies, lipids, and thyroid function will be performed by each study center's local laboratory.

The following laboratory tests will be performed at the laboratories listed below:

Cytokines, complement factor Bb, anti-PEG antibody formatio
 Tryptase

Additional laboratory tests may be performed centrally, depending upon the capabilities of the local laboratory.

Prior to study drug administration, samples for clinical laboratory tests are to be collected and results of serum chemistries, hematology, LFTs, and coagulation parameters (where applicable) reviewed and approved by the Investigator or qualified designee (e.g., physician's assistant, nurse practitioner).

In the event of an unexplained clinically relevant abnormal laboratory test occurring after study drug administration, the test should be repeated and followed up at the discretion of

the Investigator until it has returned to the normal range or stabilized, and/or a diagnosis is made to adequately explain the abnormality.

The following clinical laboratory parameters are to be determined:

Hematology	
Hematocrit	• Neutrophils, absolute and %
• Hemoglobin	• Lymphocytes, absolute and %
• Red blood cell (RBC) count	
 
Monocytes, absolute and %
 

• White blood cell (WBC) count	• Eosinophils, absolute and %
Mean corpuscular volume	• Basophils, absolute and %
Mean corpuscular hemoglobin	• Platelet count
Mean corpuscular hemoglobin concentration	
Serum Chemistries a	
• Sodium	• Glucose
• Potassium	• Phosphate
• Blood urea nitrogen (BUN)	• Lactate dehydrogenase (LDH)
• Creatinine	• Troponin I
• C-reactive protein (CRP)	• Creatinine phosphokinase (CPK)
• Albumin	• Myocardial band enzymes of CPK
• Calcium	(CPK-MB)
Liver Function Tests	
• Aspartate transaminase (AST)	Alkaline phosphatase
Alanine transaminase (ALT)	Bilirubin (total and direct)
Thyroid Function Tests	
Thyroid stimulating hormone (TSH)	Triiodothyronine (T3)
• Thyroxine (T4)	
Coagulation Studies	
Prothrombin time (PT)	International normalized ratio (INR)

 
Activated partial thromboplastin time (aPTT)
 
	

Se	rol	nσ	v
SC	נט ו	υŁ	٧

- Anti-PEG antibody formation (IgG and IgM) Hepatitis C (anti-HCV Ab)
- Hepatitis B (HBsAg and HBsAb)

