3.2. General Methods

All data listings that contain an evaluation date will contain a relative study day. Pre-treatment and on-treatment study days are numbered relative to the day of study medication dosing, which is designated as Day 0. For example, the day prior to study medication will be Day -1 and the day after study medication will be Day 1.

All output will be incorporated into Microsoft Word or Excel files, or Adobe Acrobat PDF files, sorted and labeled according to the International Conference on Harmonisation (ICH) recommendations, and formatted to the appropriate page size(s).

Tabulations will be produced for appropriate demographic, baseline, efficacy, and safety parameters. For categorical variables, summary tabulations of the number and percentage of subjects within each category (with a category for missing data) of the parameter will be presented. For continuous variables, the number of subjects, mean, median, standard deviation (SD), minimum, and maximum values will be presented.

All data will be presented in by-subject data listings.

As this is a Phase 2 dose-escalation trial, formal statistical hypothesis testing will not be performed. Although exploratory confidence intervals (CIs) will be presented as described below, no formal statistical conclusions will be made based on these estimates.

Subjects will be analyzed in the cohort to which they were originally assigned. Data will be tabulated for each dose group (i.e., dose level, regimen, and pre-medication regimen).

Laboratory data collected and recorded as below the limit of detection will be set equal to the lower limit of detection for the calculation of summary statistics.

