3.10. Missing, Unused, and Spurious Data

In general, there will be no substitutions made to accommodate missing data points. All data recorded on the case report form (CRF) will be included in data listings that will accompany the CSR. Data collected at multiple time points throughout the study will be presented in chronological order in the data listings according to assessment date/time.

Handling of partial dates for determining whether an AE is treatment-emergent is discussed in [Section 4.5.2](#). Handling of partial dates for determining concomitant medication is discussed in [Section 4.5.6](#).

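### SAP 4.5.3 divides by the detection limit when the pre-dose value lies below it, so some fold changes are lower bounds shown as exact values

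*SAP*

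**What the plan says.** SAP 4.5.3 gives the definition "Fold change from pre-dose is defined as the ratio of the post-dose value to the pre-dose value" and, for the plotted quantity, "Maximum fold change is defined as the ratio of the maximum post-dose value to the pre-dose value". The below-detection rule stands in the same paragraph: "Data recorded as below the limit of detection will be set equal the lower limit of detection for the calculation of fold change". SAP 3.2 has the matching rule for all laboratory summaries: "Laboratory data collected and recorded as below the limit of detection will be set equal to the lower limit of detection".

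The outputs differ by analyte. Fold change is tabulated for CRP and Bb. For cytokines the tables give values and change from pre-dose, but no fold change. All three have a per-subject plot of maximum fold change on a log scale, separately for Dose 1 and Dose 2 (Figures 14.3.7 to 14.3.9).

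Neither SAP 3.2, SAP 4.5.3 nor the figure titles asks for a flag, a bound sign or a count of substituted values. SAP 3.10 does say "All data recorded on the case report form (CRF) will be included in data listings that will accompany the CSR", so the recorded results can be looked up by subject.

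Protocol 7.2.7 has a list of tests that includes CRP and ends "thyroid function will be performed by each study center's local laboratory". SAP Listing 16.2.8.6 is accordingly titled as a local laboratory assessment. Protocol 7.2.7 lists cytokines and Bb separately, under specified laboratories. The synopsis allows up to 10 centers. Neither document states a detection limit for any analyte, a common CRP limit or a harmonisation rule.

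**The concern.** A below-LOD result says only that the true value lies somewhere under the limit. In a numerator, replacing it with the LOD gives the largest value it could have. In a denominator, the same replacement gives the smallest ratio compatible with the data whenever the post-dose value is detectable. A rise from an undetectable to a detectable level is therefore shown at its minimum possible size, with nothing on the plot or in the table to say so.

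Change in CRP, cytokines and complement is a named safety evaluation in SAP 1.2.5.2, and safety is the primary objective. With 3 patients in a cohort, one unmarked bound is a third of the points in that cohort. A point at 1 can mean either that a measured value did not change or that neither value could be quantified, and the reader cannot tell which. For CRP the limit itself may differ between centers, so the same true rise can appear at different heights depending on where the patient was treated.

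**Working it through.** **Inputs from the documents.** Fold change and maximum fold change are post-dose over pre-dose, and below-LOD values are set to LOD on both sides (SAP 4.5.3). CRP is measured locally (Protocol 7.2.7), at up to 10 centers (synopsis). The plan gives no figure to reproduce. Every number below is an assumption chosen to show how the rule behaves.

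**Formula.** With L for the LOD and post for the post-dose value (the largest one, for the maximum fold change):

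reported = max(post, L) / max(pre, L); true = post / pre.

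**Four cases.**

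1. Both values detectable: reported = true.
2. pre < L ≤ post: reported = post/L = true × (pre/L). Since pre/L < 1, the reported value is always too low and is a lower bound. A true 4-fold rise is reported as 4 × 0.75 = 3.0 when pre is 0.75 L, 4 × 0.5 = 2.0 at 0.5 L, and 4 × 0.25 = 1.0 at 0.25 L. A true 10-fold rise is reported as 7.5, 5.0 and 2.5.
3. Both below L: reported = L/L = 1, whatever happened. A move from 0.2 L to 0.8 L (true 4.0) and one from 0.8 L to 0.2 L (true 0.25) both give 1.
4. post < L ≤ pre: reported = L/pre, an upper bound. With pre = 4 L and post = 0.4 L, the true ratio is 0.10 and the reported ratio is 0.25. The reported value never exceeds 1, so this case cannot hide a rise.

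**Group level, varying the share below LOD.** Pre-dose values lognormal (log-SD 1.0), within-subject noise 0.4 on the log scale, geometric means reported under the rule:

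| Pre-dose below LOD | True 4-fold | True 9-fold |
|---|---|---|
| 10% | 3.83 | 8.59 |
| 25% | 3.49 | 7.76 |
| 50% | 2.82 | 6.08 |
| 75% | 2.07 | 4.10 |

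With no true change the result is 1.02 to 1.03, which is no material bias.

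**Group level, varying where the pre-dose median sits.** Pre-dose values lognormal (log-SD 0.6), every patient truly rising 5-fold:

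| Pre-dose median / LOD | Reported geometric mean | Plotted at exactly 1 |
|---|---|---|
| 0.1 | 1.04 | 88% |
| 0.25 | 1.44 | 35% |
| 0.5 | 2.45 | 6% |
| 1.0 | 3.94 | 0% |
| 2 | 4.82 | none |
| 3 | 4.96 | none |
| 5 | 5.00 | none |

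The 1.0 row can be checked by hand. If post-dose values are practically always detectable, the mean log error is the mean of min(0, ln(pre/L)), which is −0.6 × 0.399 = −0.239 when the median equals L. Then 5 × exp(−0.239) = 3.94.

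**CRP by site.** Take one patient whose CRP goes from 1 to 8 mg/L.

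| Local LOD (mg/L) | Reported fold change | Absolute change after the SAP 3.2 substitution (mg/L) |
|---|---|---|
| 0.3 | 8/1 = 8.0 | 8 − 1 = 7 |
| 3 | 8/3 = 2.7 | 8 − 3 = 5 |
| 5 | 8/5 = 1.6 | 8 − 5 = 3 |

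Both summaries depend on the local limit; the absolute change depends on it less strongly.

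**The case against.** The strongest reply is that little rides on these displays. SAP 4.5.3 already summarises values and change from pre-dose for CRP, cytokines and Bb at each time point, and it adds individual and mean plots over time and full listings. A rise from undetectable to detectable appears in all of these. The analyses are descriptive, and neither the dose-limiting toxicity criteria nor the stopping rule uses fold change. A patient plotted at 1 from an undetectable pre-dose level never had a post-dose value above the LOD, so no quantified rise is hidden there. All of this stands, and it limits the point to how certain ratios are labelled.

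Several stronger readings are tempting, and the documents do not support them.

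- *That the rule understates fold changes in general, or always pushes them down.* Only case 2 is guaranteed to be understated. Case 3 has unknown direction, and case 4 is overstated.
- *That fold change is the SAP's main measure of immune activation.* SAP 1.2.5.2 names change from baseline, and the SAP does not rank fold change above the other summaries.
- *That undetectable pre-dose values are likely.* The samples are drawn within 10 minutes before dosing and after dexamethasone, but the documents do not say what values to expect.
- *That site differences in CRP will look like dose differences.* They could, if local limits differ and values fall below them. The documents show neither.

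**Conclusion.** The point holds as one about presentation. The rule turns a below-LOD pre-dose value followed by a detectable post-dose value into a lower bound equal to the true ratio times pre-dose/LOD. That bound is shown as exact in the maximum fold-change plots for cytokines, Bb and CRP and in the fold-change tables for CRP and Bb. Where both values are below LOD, the 1 that is shown carries no information. For CRP the substituted denominator can also vary by local laboratory.

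The size cannot be fixed. Under the assumptions tried, a true 5-fold rise is reported as anything from 1.04 (median far below LOD) to 5.00 (median well above it). The effect may be negligible, particularly for Bb. No stopping rule or hypothesis test is affected. The change is worth making because it is cheap and concerns a named safety evaluation, not because the documents show a material distortion.

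A reader might also infer that reporting the median and range, or leading with absolute CRP change, would cure the problem. SAP 3.2 already provides for median, minimum and maximum, and absolute CRP change is already planned. Under the same substitution, absolute change still moves with the local LOD (7, 5 or 3 mg/L in the example), so neither request would remove the dependence.

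**What to change.** Keep the substitution and add the following to SAP 4.5.3.

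- A fold change with a below-LOD pre-dose value and a detectable post-dose value is a lower bound. Show it as ≥ x in listings and with an upward-arrow symbol in Figures 14.3.7 to 14.3.9.
- A fold change with both values below LOD is marked as not evaluable.
- The number of each is reported per dose group, separately for Dose 1 and Dose 2.
- The CRP detection limit is listed for each local laboratory.

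The cost is a few lines of SAP wording, a flag in the programming, and collecting the CRP limits from the local laboratories. No new samples or visits are needed. The downside is that some points are shown as bounds or as not evaluable rather than as exact values.
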